8.3 Recommended dose of protocol treatment

The dose will be calculated based on the body surface area (calculated using the DuBois & DuBois formula) and body weight at the time of study entry. Dose for panitumumab is round down in unit of 10 mg for reference, TAS-102 will be as Table 8.b and 8.c. At the time of entry, the data center will announce the reference dose and this should be recalculated and confirmed at the study site. The dose should be recalculated for 10% change in body weight, in principle, but at the discretion of the investigator or the subinvestigator. If more than 10% change in body weight is observed further after the recalculation the same method should be taken. However, TAS-102 dosage will be adjusted by course and adjustment from the middle of the course will not be conducted. Even if suspended during treatment period, drug will not be re-taken and drug will be taken according to stipulated treatment schedule (after 1 to 5 days, 8 to 12 days from initial administration of each course). Also, if subject missed any dose, remaining drug should not be taken.

Table 8.b TAS-102 dosage

TAS-102 dosage (twice daily)	Body surface area (m ²)	One dose (mg)	Dose per day (mg)	One dosage	
				15 mg tablet	20 mg tablet
35 mg/m ² (70 mg/m ² /day)	< 1.07	35	70	1	1
	1.07 – 1.22	40	80	0	2
	1.23 – 1.37	45	90	3	0
	1.38 – 1.52	50	100	2	1
	1.53 – 1.68	55	110	1	2
	1.69 – 1.83	60	120	0	3
	1.84 – 1.98	65	130	3	1
	1.99 – 2.14	70	140	2	2
	2.15	75	150	1	3

Table 8.c TAS-102 dosage when dose is adjusted

TAS-102 dosage (twice daily)	Body surface area (m ²)	One dose (mg)	Dose per day (mg)	One dosage	
				15 mg tablet	20 mg tablet
Drug reduction (35 mg/m² to 30 mg/m²)					
30 mg/m² (60 mg/m²/day)	< 1.09	30	60	2	0
	1.09 – 1.24	35	70	1	1
	1.25 – 1.39	40	80	0	2
	1.40 – 1.54	45	90	3	0
	1.55 – 1.69	50	100	2	1
	1.70 – 1.94	55	110	1	2
	1.95 – 2.09	60	120	0	3
	2.10 – 2.28	65	130	3	1
	2.29	70	140	2	2
	Drug reduction (30 mg/m² to 25 mg/m²)				
25 mg/m² (50 mg/m²/day)	< 1.10	25	50	2 (after dinner)	1 (after breakfast)
	1.10 – 1.29	30	60	2	0
	1.30 – 1.49	35	70	1	1
	1.50 – 1.69	40	80	0	2
	1.70 – 1.89	45	90	3	0
	1.90 – 2.09	50	100	2	1
	2.10 – 2.29	55	110	1	2
	2.30	60	120	0	3
Drug reduction (25 mg/m² to 20 mg/m²)					
20 mg/m² (40 mg/m²/day)	< 1.14	20	40	0	1
	1.14 – 1.34	25	50	2 (after dinner)	1 (after breakfast)
	1.35 – 1.59	30	60	2	0
	1.60 – 1.94	35	70	1	1
	1.95 – 2.09	40	80	0	2
	2.10 – 2.34	45	90	3	0
	2.35	50	100	2	1

*: If TAS-102 is to be given 50 mg/day, 20 mg will be given after breakfast, 30 mg after dinner.

[figure not shown]
8.4 Criteria for administration

In principle, the day (Day 29) that is 4 weeks after the starting day of treatment (Day 1) in the previous course will be Day 1 of the subsequent course (however, if the actual starting day is the next morning, the day before the starting day will be Day 1). Postponement or acceleration due to

holidays is allowed. See "Table 9.c Allowance range for protocol treatment and laboratory tests".

It should be confirmed that all of the criteria for initiation of protocol treatment (Table 8.d, Table 8.e) are satisfied on the starting day of treatment of each course. However, the latest data obtained from 2 days before treatment to the starting day of treatment may be used as test value.

Treatment will be postponed when any of the criteria for each drug is not met, and will be started after confirming that the symptom and laboratory data satisfy all of the criteria, and if only one drug satisfies the criteria for start of treatment then monotherapy with that drug may be allowed. However, at the starting point of the second course of the phase I part, both drugs are required to meet the treatment initiation criteria. If start of treatment with TAS-102 is postponed, the starting day thereafter (if the actual starting day is next morning, the day before) will be Day 1 of the course and that will be the schedule starting point, and if treatment with TAS-102 is determined to be discontinued and monotherapy with panitumumab is to be continued, the starting day of monotherapy with panitumumab will be defined as the start of course (Day 1), and the course will be defined as to give panitumumab on Day 1 and Day 15 between Day 1 and Day 28. However, while monotherapy with panitumumab is ongoing and treatment does not start beyond 42 days from scheduled start of treatment (starting day of treatment of previous course as Day 1, if treatment does not start by Day 57), protocol treatment will be discontinued. Postponement of start of treatment due to holidays is allowed.

Also, if start of treatment with panitumumab is postponed or discontinued, the starting day of treatment with TAS-102 (if the actual starting day is next morning, the day before) will be Day 1 of the course and that will be starting point for the schedule thereafter. However, while monotherapy with TAS-102 is ongoing and treatment does not start beyond 28 days from scheduled start of

treatment (starting day of treatment of previous course as Day 1, if treatment does not start by Day 57), protocol treatment will be discontinued. Postponement of start of treatment due to holidays is allowed.

[figure not shown]

Table 8.d. Criteria for initiation of treatment with panitumumab

Item	Criteria for initiation
Skin symptom (e.g., rash acneiform, dry skin, paronychia)	\leq Grade 2
Hypomagnesaemia *	\leq Grade 2
Treatment may be postponed when suspension is needed at the discretion of the investigator or the subinvestigator due to adverse events not listed above.	

*: When accompanied by abnormal ECG findings requiring treatment such as significant QTc prolongation, discontinuation or suspension of panitumumab should be considered irrespective of the severity of hypomagnesaemia.

Table 8.e Criteria for initiation of treatment with TAS-102

Item	Criteria for initiation
Hemoglobin concentration	\geq 8.0 g/dL
Neutrophil count	$\geq 1.5 \times 10^3 \mu\text{L}$
Platelet count	$\geq 7.5 \times 10^4/\mu\text{L}$
Total bilirubin	$\leq 1.5 \text{ mg/dL}$
AST	$\leq 100 \text{ IU/L}$
ALT	($\leq 200 \text{ IU/L}$ with liver metastasis)
Serum creatinine	$\leq 1.5 \text{ mg/dL}$
Peripherial sensory neuropathy	\leq Grade 2
Other non-hematological toxicity	(excluding alopecia, dygeusia, pigmentation, underlying disease related symptoms) \leq Grade 1

Treatment may be postponed when suspension is needed at the discretion of the investigator or the subinvestigator due to adverse events not listed above.

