8.5 Criteria for protocol treatment change

8.5.1 Criteria for suspension/dose reduction of panitumumab

The criteria for suspension/dose reduction and doses of panitumumab are shown in Table 8.f and Table 8.g, respectively.

Table 8.f Criteria for suspension/dose reduction of panitumumab

Item	Grade	Dose adjustment for the next dose of panitumumab
Skin disorder	≥ 3	Dose reduction by 1 level after suspension However, treatment at a dose of 6 mg/kg is allowed without dose reduction when it recovers to Grade 2 or less within 6 weeks (42 days) .
Hypomagnesaemia *	≥ 3	
Pulmonary fibrosis (interstitial pneumonia)	≥ 2	Discontinue protocol treatment
Infusion reaction (reaction from injection) **, ***	≥ 3	Discontinuation (no resumption)

Dose reduction/suspension is allowed as necessary at the discretion of the investigator or the subinvestigator due to adverse events not listed above.

*: When accompanied by abnormal ECG findings requiring treatment such as significant QTc prolongation, discontinuation or suspension of panitumumab should be considered irrespective of the severity of hypomagnesaemia.

**: Allergic reaction, anaphylactoid reaction, and chills, fever, and dyspnea occurring within 24 hours after the initial dose

***: If infusion reaction is observed, immediately discontinue administration. The course may be resumed at the discretion of the study site. In the event that Grade 1 or 2 infusion reaction occurs during infusion, careful administration will be allowed after appropriate supportive therapy has been given or infusion speed has been decreased by 50%, etc., upon administration of subsequent course.

Table 8.g Doses of panitumumab

Dose reduction level	Panitumumab
Initial dose	6 mg/kg
-1	4.8 mg/kg
-2	3.6 mg/kg
-3	Discontinuation (no resumption)

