The administration of panitumumab may be postponed (skipped) and only TAS-102 therapy performed when the subject meets the panitumumab suspension criteria (in this case, the day of starting the next course (Day 1) will be the day of starting TAS-102 therapy). When the actual day of initiating administration starts on the morning of the next day, the day before starting administration will be Day 1. For the next dose of panitumumab, treatment will be resumed after it is confirmed that the subject does not meet the criteria for suspension of panitumumab, but if panitumumab cannot be administered for more than 28 days after the scheduled day of treatment initiation, panitumumab treatment will be discontinued.

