TAS-102 treatment will be resumed after it is confirmed that the subject meets the criteria for initiation of TAS-102 treatment (however, when the subject satisfies the criteria for initiation of treatment from Day 13 to Day 28 of the suspension period, treatment will be resumed on Day 29). However, if TAS-102 cannot be administered for more than 28 days from the scheduled day of initiation of treatment, treatment with TAS-102 will be discontinued. (At this time, the day of initiating panitumumab monotherapy after it is determined that treatment with TAS-102 will be discontinued will be defined as the day for starting the course (Day 1), and the course will be defined as the administration of panitumumab between Day 1 and Day 28 on Days 1 and 15.)

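### Protocol 8.4 gives the panitumumab-monotherapy stopping limit as both 42 days from scheduled start (Day 71) and Day 57; the other delay rules support 28 days and Day 57

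*Protocol*

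**What the plan says.** Section 8.4 of the Protocol counts the start of the previous course as Day 1 and schedules the next course for Day 29. Table 9.c agrees.

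For a subject who has stopped TAS-102 and continues on panitumumab alone, "the course will be defined as to give panitumumab on Day 1 and Day 15 between Day 1 and Day 28". Protocol treatment then ends if "treatment does not start beyond 42 days from scheduled start of treatment". The bracket that follows, with the previous course's start as Day 1, gives the condition as "if treatment does not start by Day 57".

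The parallel sentence for a subject on TAS-102 alone applies "while monotherapy with TAS-102 is ongoing and treatment does not start beyond 28 days from scheduled start of" treatment, and its bracket is the same: "if treatment does not start by Day 57), protocol treatment will be discontinued".

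Four other places bear on how long a delay may last:

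- Section 8.5.1 stops panitumumab "if panitumumab cannot be administered for more than 28 days after the scheduled day of treatment initiation".
- Section 8.5.2 stops TAS-102 "if TAS-102 cannot be administered for more than 28 days from the scheduled day of initiation of treatment".
- Section 8.9.1 uses Day 57 for a phase I subject who cannot start Course 2 because of adverse events.
- Section 8.7, item 2, ends protocol treatment when an adverse event postpones it for 58 days or more after the last course began.

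Table 8.f in Section 8.5.1 also has a 42-day figure for panitumumab. It lets the full dose resume after a skin disorder or hypomagnesaemia "when it recovers to Grade 2 or less within 6 weeks (42 days").

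**The concern.** The interval and the day number in the panitumumab sentence are offered as the same limit, yet they do not agree when counted from the origin the sentence names. This is an operative rule that decides whether protocol treatment ends, and about 30 phase II sites have to apply it. Two sites could treat the same delay differently, each with support from the text.

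The analysis quantity at stake is TTF. The decision to discontinue protocol treatment is one of its events (Protocol 13.3.3.2; SAP 7.2.4.2, item 6), so a different reading of the rule can change an event date.

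**Working it through.** **Inputs**

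- Scheduled start of the next course: 1 + 28 = Day 29 (Protocol 8.4; Table 9.c).
- Panitumumab-alone rule: 42 days from scheduled start; bracket Day 57 (8.4).
- TAS-102-alone rule: 28 days from scheduled start; bracket Day 57 (8.4).
- Panitumumab dosing days: Day 1 and Day 15 of each course (8.4).

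**Formula:** last permitted start day = origin day + allowed delay.

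**Step 1. The rule that reproduces.** TAS-102 alone: 29 + 28 = Day 57. Interval and bracket agree.

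**Step 2. The rule that does not.** Panitumumab alone: 29 + 42 = Day 71. The bracket says Day 57. The gap is 71 − 57 = 14 days.

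**Step 3. Does another origin rescue the 42?**

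| Origin | Origin + 42 |
|---|---|
| Day 1 (previous course start) | Day 43 |
| Day 15 (mid-course panitumumab dose) | Day 57 |
| Day 28 (last day of course) | Day 70 |
| Day 29 (scheduled start, as stated) | Day 71 |
| Day 29 with the ±3-day window (Days 26 to 32) | Days 68 to 74 |

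Only Day 15 gives Day 57. The sentence names the scheduled start of treatment, which 8.4 places at Day 29.

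**Step 4. What the other rules support.**

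- 8.5.1 and 8.5.2: 28 days from the scheduled day. For a course due on Day 29, 29 + 28 = Day 57.
- 8.9.1: Day 57, stated directly.
- 8.7, item 2: 58 days or more after the last course start. With the start as Day 1 this is Day 58, the first day past Day 57. In elapsed days it is 1 + 58 = Day 59. It therefore matches Day 57 to within a day.
- Table 8.f: its 42 days is a recovery window governing dose reduction. It is not a limit for ending protocol treatment.

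No other delay rule leads to Day 71.

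**Step 5. Who could be affected.** A subject on panitumumab alone who is first able to restart on Days 58 to 71 is stopped by the bracket and kept on by the 42-day wording. Most such subjects are caught elsewhere. Section 8.5.1 discontinues panitumumab after 28 days, which leaves a monotherapy subject with no protocol drug, and 8.7 item 2 stops delays caused by adverse events. What remains is a delay due neither to an adverse event nor to a holiday, at a site that reads 8.5.1 as limited to its own suspension criteria. The documents give no size for that group.

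**The case against.** The strongest reply is that the figures can be reconciled: Day 15 is a scheduled panitumumab day, Table 9.c lists Days 1, 15 and 29 as treatment days, and 15 + 42 = 57. On this view only the origin is unclear. The bracket also supplies its own origin and endpoint, so a site can apply it without using the 42, and 8.5.1 and 8.7 item 2 act as backstops.

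Much of this stands. The Day 15 count is a plausible source of the figure, the bracket is explicit, and the practical effect is small. But reconciling the figures requires replacing the sentence's stated origin with one it does not mention, so the sentence needs correcting on either account.

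It is also fair to say that Day 57 may not have been intended. The 42 could have been deliberate for panitumumab, with the bracket carried over from the TAS-102 sentence. The other rules make this less likely but do not exclude it. A figure after these rules is not shown in the copy reviewed; it might show how the count was meant, but it would not make 29 + 42 equal 57. The wording is not a PDF-reading fault, because the earlier protocol version in the same file has the same pair of figures.

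**Conclusion.** Wrong as written, and minor. Counted in elapsed days from the Day 29 scheduled start, and leaving aside holiday shifts, one sentence sets limits at Day 71 and Day 57, 14 days apart. Day 57 is the better-supported limit.

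A reader might infer three stronger things that the documents do not support:

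- *TTF can move by at most 14 days.* The 14 days separates two restart limits. A subject allowed to restart stays on treatment until a later discontinuation, progression or death, so the change in TTF has no such cap and the documents do not bound it.
- *Day 57 is certainly what was meant.* It is the best-supported limit; only the sponsor can confirm it.
- *The primary result is at risk.* The 6-month PFS rate is not directly affected, because stopping treatment is not a cut-off for progression status (Protocol 13.3.3.2; SAP 7.2.4.1). Alpha and sample size are likewise not directly affected.

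The judgement that few subjects are likely to be affected rests on 8.5.1 and 8.7 item 2 being applied as written, since no count is available.

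**What to change.** Ask the sponsor to confirm that Day 57 is the intended limit. Then, in the panitumumab-monotherapy sentence of Section 8.4, change 42 days to 28 days and keep Day 57. The sentence will then agree with its TAS-102 counterpart and with 8.5.1, 8.5.2 and 8.9.1.

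Do not repair it by counting 42 days from the last panitumumab dose. Section 8.5.1 allows a dose to be skipped; if Day 15 was missed, the last dose was Day 1, and 1 + 42 = Day 43, which creates a new conflict with Day 57.

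The cost is one figure in a clarification to sites. Sample size and planned analyses do not change.

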8.5 Criteria for protocol treatment change

8.5.1 Criteria for suspension/dose reduction of panitumumab

The criteria for suspension/dose reduction and doses of panitumumab are shown in Table 8.f and Table 8.g, respectively.

Table 8.f Criteria for suspension/dose reduction of panitumumab

Item	Grade	Dose adjustment for the next dose of panitumumab
Skin disorder	≥ 3	Dose reduction by 1 level after suspension However, treatment at a dose of 6 mg/kg is allowed without dose reduction when it recovers to Grade 2 or less within 6 weeks (42 days) .
Hypomagnesaemia *	≥ 3	
Pulmonary fibrosis (interstitial pneumonia)	≥ 2	Discontinue protocol treatment
Infusion reaction (reaction from injection) **, ***	≥ 3	Discontinuation (no resumption)

Dose reduction/suspension is allowed as necessary at the discretion of the investigator or the subinvestigator due to adverse events not listed above.

*: When accompanied by abnormal ECG findings requiring treatment such as significant QTc prolongation, discontinuation or suspension of panitumumab should be considered irrespective of the severity of hypomagnesaemia.

**: Allergic reaction, anaphylactoid reaction, and chills, fever, and dyspnea occurring within 24 hours after the initial dose

***: If infusion reaction is observed, immediately discontinue administration. The course may be resumed at the discretion of the study site. In the event that Grade 1 or 2 infusion reaction occurs during infusion, careful administration will be allowed after appropriate supportive therapy has been given or infusion speed has been decreased by 50%, etc., upon administration of subsequent course.

Table 8.g Doses of panitumumab

Dose reduction level	Panitumumab
Initial dose	6 mg/kg
-1	4.8 mg/kg
-2	3.6 mg/kg
-3	Discontinuation (no resumption)

The administration of panitumumab may be postponed (skipped) and only TAS-102 therapy performed when the subject meets the panitumumab suspension criteria (in this case, the day of starting the next course (Day 1) will be the day of starting TAS-102 therapy). When the actual day of initiating administration starts on the morning of the next day, the day before starting administration will be Day 1. For the next dose of panitumumab, treatment will be resumed after it is confirmed that the subject does not meet the criteria for suspension of panitumumab, but if panitumumab cannot be administered for more than 28 days after the scheduled day of treatment initiation, panitumumab treatment will be discontinued.

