Study population: patients with RAS wild-type unresectable, advanced/recurrent colorectal cancer refractory or intolerant to fluoropyrimidines, oxaliplatin, irinotecan and angiogenesis inhibitors (bevacizumab, afibbercept, ramycirumab, etc.)

Planned number of subjects:

A maximum of 58 subjects

CONFIDENTIAL

Number of study sites:

Phase I part: approximately 5

[figure not shown]
Phase II part: approximately 30

Method of administration:

Treatment for 4 weeks (28 days) as 1 course according to the dosage, schedule and route of administration as follows.

Panitumumab: 6 mg/kg/dose once each on Day 1 and Day 15 by IV administration (IV drip infusion)

TAS-102: 35 mg/m²/dose given orally twice daily (after breakfast and after dinner) for 5 consecutive days followed by 2 days of washout and after this is repeated twice, 14 days washout will be implemented.

If either panitumumab or TAS-102 or both drugs are to be reduced for DLT occurrence in phase I part, dosage and administration will be as follows.

If panitumumab is to be reduced: 4.8 mg/kg/dose once each on Day 1 and Day 15 by IV administration (IV drip infusion)

If TAS-102 is to be reduced: 30 mg/m²/dose given orally twice daily (after breakfast and after dinner) for 5 consecutive days followed by 2 days of washout and after this is repeated twice, 14 days washout will be implemented.

Dose limiting toxicity (DLT) definition

In this study, DLT will be assessed based on the adverse events observed in 6 subjects at maximum enrolled in phase I part. DLT will be defined as follows [definition and grade will be based on Common Terminology Criteria for Adverse Events (CTCAE) ver4.03]. Further, DLT will be assessed from Day 1 of course 1 of protocol treatment, and if DLT does not occur by Day 1 of course 2, it will be handled as no occurrence of DLT in the subject. Adverse events that can clearly be denied of causal relationship with the protocol treatment will not be assessed as DLT. If serious adverse event or unexpected adverse event occurs which causal relationship with the protocol treatment cannot be denied other than the following, it may be determined as to whether or not to handle it as DLT in consultation with the Investigator, the Research Steering Committee and the sponsor.

1. Persistent Grade 4 neutropenia for more than 7 days under maximum supportive therapy
2. Febrile neutropenia
3. Blood platelet decreased of Grade 3 requiring platelet transfusion or blood platelet decreased of Grade 4

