6.0 CLINICAL STUDY DESIGN

6.1 Clinical study design

This phase I/II study is a multi-center, open-label single-arm study that consists of a phase I part (dose de-escalation) which will assess the tolerability and RD of Panitumumab in combination with TAS-102 as primary objective, and a phase II part which will assess the efficacy and safety of Panitumumab in combination with TAS-102 as primary objective in patients with RAS wild-type unresectable, advanced/recurrent colorectal cancer. In the phase I part, the subjects will be included sequentially into Cohort 1 and 2, 3 subjects each with the same dosage and administration. In the phase II part, 46 subjects will be included additionally for RD confirmed in the phase I part.

[figure not shown]

Figure 6.a Outline of study design

In the phase I part, each cohort will be conducted with 3 subjects, the sponsor will assess tolerability of the dosage and administration based on the incidence of Dose Limiting Toxicity (hereinafter referred to as DLT) during the assessment period and determine whether or not to move on to the next cohort (opinion from the Data Monitoring Committee [hereinafter referred to as DMC] will be confirmed appropriately upon determination). Therefore, in Cohort 1, if occurrence of DLT is ≤ 2 subjects out of 3, the dosage and administration will be determined tolerable and will move on to Cohort 2. However, if DLT is observed in 2 subjects during DLT assessment period in Cohort 1, subjects will be included one at a time in Cohort 2 in consideration for safety to assess DLT.

CONFIDENTIAL

Similarly 3 subjects will be included in Cohort 2 and DLT will be assessed in a total of 6 subjects of Cohort 1 and 2 at most. If DLT is observed in 3 subjects included in Cohort 1, or DLT is observed in 3 subjects from a total of 6 subjects of Cohort 1 and 2, the sponsor will promptly request to postpone new enrollment of subjects to each site and after consultation with the Research Steering Committee and DMC on the continuation of the study, will determine whether or not to continue the study.

If study is to be continued, taking in account of the adverse event that occurred, either panitumumab or TAS-102 or both drugs will be reduced one step and re-conducting the phase I part similarly will be considered. If DLT is observed in 3 subjects after reducing 1 step of panitumumab or TAS-102 or both drugs, the study will be discontinued.

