8.6 Criteria for dose increase of protocol treatment

The dose should not be increased after dose reduction for any of the drugs.

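### Table 8.f fixes its recovery exception at 6 mg/kg without saying whom it covers or when its 42 days start, and it is not reconciled with section 8.6, a reduced recommended dose or the 28-day limit

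*Protocol*

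**What the plan says.** Table 8.f in protocol section 8.5.1 governs the next panitumumab dose after a Grade 3 or higher skin disorder or hypomagnesaemia. The default is relative to the dose ladder: "Dose reduction by 1 level after suspension". The exception in the same cell is absolute: "However, treatment at a dose of 6 mg/kg is allowed without dose reduction when it recovers to Grade 2 or less within 6 weeks". The wording is the same in both protocol versions in the file. In the text as read the hypomagnesaemia cell is blank; I take it as merged with the skin-disorder cell.

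Four other provisions bear on this cell:

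- Table 8.g sets the ladder at 6, 4.8 and 3.6 mg/kg, then discontinuation.
- Section 8.6 says: "The dose should not be increased after dose reduction for any of the drugs". It makes no exception for Table 8.f.
- Section 6.1 foresees that, after too many dose-limiting toxicities, "either panitumumab or TAS-102 or both drugs will be reduced one step and re-conducting the phase I part similarly will be considered". The study summary gives the dose for that branch: "If panitumumab is to be reduced: 4.8 mg/kg/dose once each on Day 1 and Day 15 by IV administration". Phase II then follows whatever phase I confirms: "In the phase II part, 46 subjects will be included additionally for RD confirmed in the phase I part".
- The text below Table 8.g limits the interruption: "if panitumumab cannot be administered for more than 28 days after the scheduled day of treatment initiation, panitumumab treatment will be discontinued". Panitumumab resumes only once the suspension criteria are no longer met, which for these two rows means Grade 2 or less.

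**The concern.** A rule stated in levels and an exception stated in mg/kg sit in one cell, and the cell does not say to whom the exception applies. Subjects below 6 mg/kg can exist: the exception permits rather than requires full dose, and Table 8.f also allows discretionary reduction for other events. If such a subject has a further Grade 3 event and recovers, one site may read the cell as allowing 6 mg/kg and another as requiring a further step down. The cell also gives 42 days for recovery while the following text stops the drug after 28 days, and the two clocks are not tied to each other.

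At stake is consistent dosing after two of panitumumab's characteristic toxicities. The SAP (version 4.0) also reports relative dose intensity (7.2.3.1) and dose-reduction frequency (7.2.3.5), and both would partly reflect how each site read the cell. The overdose definition in section 10.1.2 would not flag the problem, because it counts only doses above 6 mg/kg.

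**Working it through.** The plan states no figure to reproduce here. The check is a comparison of passages with dose and day arithmetic.

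**Dose, by current level (Table 8.g), if the exception is applied literally**

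| Current dose | Change to 6 mg/kg | Against section 8.6 |
|---|---|---|
| 6 mg/kg | 6/6 = 1.00, no change | compatible |
| 4.8 mg/kg (level -1) | 6/4.8 = 1.25, +25% | forbidden |
| 3.6 mg/kg (level -2) | 6/3.6 = 1.67, +67% | forbidden |

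If phase I were repeated and the recommended dose became 4.8 mg/kg, the fixed 6 mg/kg would lie 25% above it. Section 8.6 does not clearly block this, since it speaks of increases after a reduction and a subject who started at 4.8 mg/kg has had none. Tables 8.f and 8.g are not restated for that branch.

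**Timing.** Take a subject infused on Day 1 whose Day 15 infusion is missed. Two things are unstated or unclear.

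- Start of the 42 days: from the last infusion, the window ends on Day 1 + 42 = Day 43. From the missed infusion, it ends on Day 15 + 42 = Day 57.
- Scheduled day in the 28-day limit: if it is the missed infusion, the last permitted day is 15 + 28 = Day 43, which is 14 + 28 = 42 days after the last infusion. If it is the next course's Day 1 (Day 29), the last permitted day is 29 + 28 = Day 57. Section 8.4 counts this way for course starts.

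| 42 days run from | Limit runs from missed infusion (ends Day 43) | Limit runs from next course's Day 1 (ends Day 57) |
|---|---|---|
| last infusion (ends Day 43) | both end together; every permitted resumption meets the exception, so the reduction is never mandatory at 6 mg/kg | Days 44-57: resumption permitted, exception expired, one-level reduction applies |
| missed infusion (ends Day 57) | Days 44-57, i.e. days 29-42 after the missed infusion: Table 8.f allows 6 mg/kg, the text discontinues panitumumab | both end together |

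Table 9.c allows ±3 days around each scheduled infusion, so these boundaries can move by a few days.

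**Frequency.** Table 4.c gives Grade 3 or higher skin disorders of 9.4% (monotherapy) and 15.0% (with chemotherapy). For 52 subjects: 52 × 0.094 = 4.9 and 52 × 0.15 = 7.8. This is the expected number with any such skin event. It is not the number already reduced who then have a further event that recovers in time; the documents give no basis for that count.

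**The case against.** The strongest reply is that the cell is clear in context. It is an exception to a one-level reduction and speaks of continuing with no reduction, which naturally describes a subject at 6 mg/kg who stays there. Raising someone from 4.8 mg/kg would be an increase, and section 8.6 bars increases. On that reading Table 8.f and section 8.6 agree. Treating a subject at full dose differently from one already reduced is also a coherent clinical rule. This stands, and it rules out the stronger inference that the plan grants 6 mg/kg whatever the current dose: the documents nowhere say so. What remains is that the cell does not state this limit and gives a dose in mg/kg where the rule beside it uses levels.

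A reader might also infer that phase II will exceed the recommended dose. The documents do not support that. A recommended dose of 4.8 mg/kg needs phase I to meet its toxicity limit, the study to continue, and panitumumab, not only TAS-102, to be the drug reduced. Other passages (Table 8a, section 8.9.2) also assume a 6 mg/kg start, so the gap for that branch is not confined to this cell.

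Nor can one say outright that the one-level reduction is never mandatory. That depends on how the scheduled day and the 42-day start are read; on one reading above, the reduction does apply on Days 44-57. The ±3-day allowance also breaks the exact 14 + 28 = 42 match. The objection defeats the categorical claim but confirms that the clocks need definition.

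**Conclusion.** The point holds as an internal inconsistency on a literal reading and an ambiguity on the natural one. The fixed 6 mg/kg conflicts with section 8.6 only for a subject already at 4.8 or 3.6 mg/kg, and with the recommended-dose provisions only if phase I is repeated with panitumumab lowered. The undefined 42-day window either leaves days 29-42 after a missed infusion under two opposed instructions, or can make the one-level reduction optional throughout at 6 mg/kg, or matches the 28-day limit less simply, depending on two readings the protocol does not settle.

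The number of subjects affected is not known, and the 5-8 of 52 expected to have any Grade 3 or higher skin event should not be taken for it. The sample size and the test of the 6-month PFS rate are unaffected. It should still be corrected, because sites following the same text can treat the same subject differently after a serious toxicity.

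**What to change.** Reconcile Table 8.f with Table 8.g, section 8.6, the recommended-dose provisions (study summary and section 6.1) and the 28-day limit in section 8.5.1. The revised cell should state whom the exception covers, from which day the 42 days run, and when the one-level reduction applies. The same revision should make clear which scheduled day the 28-day limit counts from. Which dose follows recovery, and under what conditions, is for the sponsor's clinical team; none is proposed here. The cost is the rewording of one table cell, by amendment or a memo to sites, with no change to sample size or analysis.
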